**Outcome Measures –**

The following measures will be used in **all children enrolled in the screening cohort**:

- 1) *TARGet Kids! child and family characteristics questionnaire* – Data on child characteristics (including socioeconomic status and ethnicity) as well as family factors (family structure, child care and familial illnesses), diet and physical activity, and health will be obtained from a detailed 60 item questionnaire (adapted from the Canadian Community Health Survey) which is completed by a parent at the time of enrolment. Questionnaires have been extensively pilot tested since September 2008, and numerous modifications have been made to ensure understandability and reduce incomplete responses.
- 2) *The Early Childhood Behavior Questionnaire (ECBQ)* – The ECBQ assesses the following dimensions in children 18-36 months: Activity level/Energy, Attentional Focusing, Attentional Shifting, Cuddliness, Discomfort, Fear, Frustration, High-intensity Pleasure, Impulsivity, Inhibitory Control, Low-intensity Pleasure, Motor Activation, Perceptual Sensitivity, Positive Anticipation, Sadness, Shyness, Sociability, Soothability. Parents are asked how often they have observed each behavior during the last two weeks, and respond on a 7-point scale (never, very rarely, less than half the time, about half the time, more than half the time, almost always, always). The Very Short Form consists of 36 items in 3 broad scales: Negative Affect (12 items), Surgency (12 items), Effortful Control (12 items). For each scale, an average is calculated, so that the child has a score for each of the 3 scales.
- 3) *Laboratory measures* – 3 mL of blood is obtained to complete all of the *TARGet Kids!* laboratory measures. This is well within the acceptable amount for this age group. The current study focuses on laboratory measures of iron status, including hemoglobin, mean corpuscular volume, and serum ferritin. (Separately funded *TARGet Kids!* studies focus on laboratory measures of vitamin D and cardiometabolic status). Standardized reference ranges will be used to determine if the result is normal or abnormal.
- 4) *Physical measurements* – Measurement of height, weight and waist circumference of subjects and their accompanying parent, along with child head circumference, is performed using standardized anthropometric protocols. Weight is measured using a precision digital scale ( $\pm 0.025\%$  SECA, Hamburg Germany) and standing height is measured using a stadiometer (SECA, Hamburg Germany). Body Mass Index (BMI) is calculated as weight in kilograms divided by height in meters squared and categorized as percentile categories using WHO Child Growth curves (which, unlike CDC growth curves, include percentiles for children under 2 years

**Trial title: Optimizing Early Child Development in the Primary Care Practice Setting: Pragmatic Randomized Trial of Iron Treatment for Young Children with Non-anemic Iron Deficiency (OptEC)**

of age and are able to monitor the rapid rate of growth in early infancy). Blood pressure is assessed according to the guidelines of the National High Blood Pressure Education Program.

**Additional measures for children enrolled into the OptEC trial**

*Mullen Scales of Early Learning (MSEL)* – The MSEL assess the cognitive functioning of young children from birth to 68 months. The assessment is based on the child's responses to activities prepared by the trained examiner. Five skill areas are measured: Gross Motor and four cognitive skills (summarized into an Early Learning Composite score) - Fine Motor, Visual Reception, Receptive Language, and Expressive Language. The raw scores for each scale can be converted into age-adjusted normalized scores. The four 'cognitive' skills score can be converted into a normalized ELC score, with a mean of 100 and a standard deviation of 15. A participant information sheet that contains information regarding developmental testing will be provided to parents who agree to participate in the trial.

**Pre-study screening and Baseline Measurements**

The baseline data for this trial will be the same data collected during the TARGet Kids! visit of a child. In the TARGet Kids! Program parents/caregivers of eligible children are invited to participate by letter two weeks before their scheduled well-child visit. At the time of the physician office visit, parents will complete the written consent form, questionnaires (*TARGet Kids!* child and family characteristics questionnaire, ECBQ) and physical and laboratory measurements as described above. The overall research plan is shown in a schematic (See Appendix 3: Schematic of study plan). A Parent Letter containing a short description of the OptEC trial will be given to parents of children enrolled in the TARGet Kids! Initiative and are potential candidate for the OptEC trial. This letter will state that in case found eligible the parents will be contacted by phone to invite them to participate in the OptEC trial.

**Recruitment Strategy**

TARGet Kids! Network has 6 collaborating primary pediatrician and family medicine practices. This trial will be integrated into the current TARGet Kids data collection system and the baseline data for this trial will be the same data collected during the TARGet Kids! visit of a child. After the physicians receive the lab test results research assistants (RA) will be instructed to contact potential participants over the phone. That the RA can contact TARGet Kids participants over the phone for participation into future studies have been incorporated into the TARGet Kids consent form. When the RA approach the parents over the phone to consider participating in this trial the RA will at the same time introduce the OptEC Trial to the parents and request them to return to the physician's office if they agree to participate. The RAs will be provided with a scripted telephone dialogue in order to standardize the patient recruitment process done over telephone. A Screening Form will be used to screen and enroll participants in the trial. At the physician's office the RA will review the consent form with the parent. The clinic nurse will review the iron status of the child with the parent and obtain informed written consent. The family will have the opportunity to ask questions to the RA, the pediatrician and/or office nurse/staff at any time.

**Participant Timeline**

**Trial title: Optimizing Early Child Development in the Primary Care Practice Setting: Pragmatic Randomized Trial of Iron Treatment for Young Children with Non-anemic Iron Deficiency (OptEC)**

Participants will be assessed at two time periods: baseline and four months after the baseline visit. The baseline assessment will be carried out in two steps. Step 1: The baseline TARGeT Kids! Data collection; Step 2: According to the lab test results those who agree to participate in the OptEC trial will be asked to come back to the physicians office where the developmental testing will be performed. Data (questionnaires, physical measurements, developmental testing and laboratory testing) will be collected at both the baseline and follow-up periods. There is no requirement for a run-in period or washout period.

**Randomization, Stratification, Blocking and Sequence Generation**

Randomization will be stratified by clinic site. Block randomization will be generated with blocks of variable sizes. An advantage of block randomization is that group sizes are similar at the end of each block enrolled. The biostatistician will generate the randomization sequence for each clinic site using computer-generated random numbers.

**Allocation Concealment**

Allocation concealment is the process that prevents any trial participant or investigator from knowing in advance the treatment to which subjects will be assigned, and seeks to prevent selection bias. In this study, allocation concealment will be achieved by having the Pharmacy Department at the Hospital for Sick Children prepare the treatment and placebo in sealed, serially numbered bottles of similar appearance and weight according to the allocation sequence. A disadvantage of block randomization is that it may lead to study personnel guessing the allocation sequence; to reduce this possibility and to enhance allocation concealment the block sizes will be varied.

**Blinding**

Parents, attending physicians, laboratory personnel, and study personnel conducting the outcome assessments, data analysts and investigators will be blind to the group allocation. Study medication and placebo will be supplied in bottles that look identical, and the appearance, consistency and taste of the liquid will be similar. Group allocation will be concealed until the final data analysis is performed.

**Non-randomized Children**

Since all children will undergo laboratory screening at baseline, two additional groups of children (IDA, IS) will be identified and followed without randomization. Children with IDA will all receive oral iron treatment 6 mg elemental iron/kg/day in 2 divided doses for four months plus dietary counseling, which would be considered standard of care. Children with iron sufficiency (IS) will not receive any intervention. Children with IDA and IS will be included in the analysis plan for comparison with the NAID groups.

**Data Collection Methods**

Questionnaire data and physical measurements will be collected by the Research Assistants who are embedded in the practices. The Research Assistants have been trained to ensure accuracy of data collection and the questionnaires have been extensively pilot tested. The TARGeT Kids! Health and Nutrition Questionnaire will be used to collect data only at baseline, a follow-up questionnaire will be used at the follow-up visit and the ECBQ will be used both at baseline and

**Trial title: Optimizing Early Child Development in the Primary Care Practice Setting:  
Pragmatic Randomized Trial of Iron Treatment for Young Children with Non-anemic Iron Deficiency (OptEC)**

follow-up visit. Blood work will be obtained by trained personnel according to the arrangements established at each of the practice sites; for example at some sites the Research Assistant is also a trained Phlebotomist and at some sites the clinic Nurse performs phlebotomy. Blood testing will be performed once during the TARGet Kids! visit and then after four months during the follow-up visit. The Research Assistant is responsible for ensuring the blood is delivered to Mount Sinai Services (MSS) for laboratory testing. MSS provides customized laboratory and research services to pharmaceutical and biotech companies, and researchers

(<http://www.mountsinaiservices.com/pages/Home>). Laboratory results are sent electronically to the data management centre (see next section) as well as faxed to the practicing physician who is responsible for communicating the results to the participants. Children eligible for the randomized trial will return to the physician's office where the Mullen Scales of Early Learning will be administered by a trained psychometrist under the supervision of one of the co-investigators who is a developmental psychologist ([name]). This will take approximately 30-40 minutes. At the 4 month follow up visit, the Research Assistant is responsible for ensuring that the questionnaires, physical and laboratory measures are completed. The psychometrist will complete the MSEL.

**Concomitant Medication**

Concomitant interventions permitted include over the counter multivitamins which do not contain iron; those prohibited include additional over the counter iron.

**Premature Withdrawal Criteria**

- 1) Participant developing hypersensitivity to the provided syrup
- 2) Participant becoming extremely sick
- 3) Participant hospitalized for more than a week without signs of improvement

**Probable lost to follow-up patients**

**Children who fail to show-up for their 4 month follow-up visit will be contacted initially on alternate days up to a period of one month and then on a monthly basis until the end of the trial period (4 years) by the RAs over telephone.**

**Unblinding Procedures**

If a subject in the randomized study deteriorates or has persistent, severe bothersome side effects then unblinding may be necessary. Emergency unblinding should only be done when the clinical treatment of the patient will be different by knowing which arm of the study the patient was on. The physician caring for the subject should contact the principal investigator or co-investigator first to discuss the unblinding procedure. The study investigators should remain blinded if possible.

**Adverse event reporting**

All adverse events will be reported to the Hospital for Sick Children Research Ethics Board according to the Hospital for Sick Children's adverse event reporting requirements. All adverse drug reactions to the study medication will be reported to Health Canada within 15 calendar days or for death or life-threatening events, within 7 calendar days. In the latter case, a follow-up

## **Trial title: Optimizing Early Child Development in the Primary Care Practice Setting: Pragmatic Randomized Trial of Iron Treatment for Young Children with Non-anemic Iron Deficiency (OptEC)**

report must be filed within 8 calendar days. Adverse reactions will be managed according to the Hospital for Sick Children's standard clinical management practices.

### **Sample Size**

From previous research, it is anticipated that the mean MSEL developmental score for children with NAID will be 90, and the standard deviation is  $\pm 15$ . To detect a 6 point difference in post-treatment MSEL developmental score between treatment and placebo group, with a power of 80% and a significance level of 5% will require a total sample size of 150 (75 per group).

With an estimated prevalence of NAID of 10%, it is anticipated that screening approximately 1500 children will identify 150 children with NAID to be randomized over a 4 year period.

Expecting potential drop-outs and withdrawals to be 0-20% a total of 180 NAID children will be randomized. For the non-randomized children (IDA and IS), it is anticipated that the mean MSEL developmental score for children with IDA will be 85 and the mean developmental score for IS children will be 100 with a standard deviation of  $\pm 15$ . From the screening cohort of 1500 it is anticipated that 1-2% will have IDA (n=25) and an equal number of randomly selected children with IS (n=25) will be sampled for comparison. To randomly select children with IS, once a child with IDA is identified the immediate next child identified with IS and agrees to participate will be enrolled in the trial.

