### **Statistical Analysis**

From the screening cohort, the baseline characteristics of the three groups (NAID, IDA, IS) will be compared with descriptive statistics and significance testing. Categorical variables will be compared with a chi-square test and that continuous variables will be compared with an ANOVA (or non-parametric equivalent). For the participants with NAID randomized to treatment or placebo groups, no significance testing will be performed on the baseline characteristics); however, we will note any imbalances that have arisen by chance which may be clinically meaningful. All children with NAID randomized to treatment or placebo will be analyzed in the group to which they were randomized following the intention to treat principle. In the primary analysis, the difference in developmental and hematologic measures in children with NAID randomized to treatment versus placebo will be assessed using linear regression (ANCOVA method) with the initial baseline measures included as the adjusting variable. In a secondary analysis, additional co-variates of clinical or statistical significance (including, parent education, family income) will be included in the model. The primary analysis will be a fixed effects model, ignoring stratification by clinic site. A secondary analysis will include a confirmatory analysis using a mixed effects model with interventions and MSEL scores as the fixed effect and clinic site as the random effects. Although efforts to ensure complete data collection and participant follow up will be maximized, analytic strategies to handle missing data will include imputation techniques, if appropriate. If >20% of participants are lost to follow-up a per protocol analysis will be carried out in addition to the intention to treat analysis.

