**Sample size:**

The minimum size for an internal pilot study should be 10 or more patients per intervention group. It has been shown that the larger the size of the internal pilot the more the accurate will be the estimates and so more appropriate will be the recalculated sample size . Thus based on these facts the sample size may be recalculated after 30 participants have been enrolled in the randomized trial.

In order to recalculate the sample size for the OptEC trial using the estimates of the internal pilot study, we will not need to break the randomization code. As discussed with the study statistician this methodology is in alignment with proper conduct of clinical trials. None of the investigators will be unblinded to subjects' group allocation.

**Sub-study #2: The effectiveness of oral iron therapy in improving the growth and haematological outcome of pre-school children with non-anemic iron deficiency (NAID): A randomized trial.**

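### The Sample Size section gives both 150 and 180 as the number to be randomized from one screening cohort of 1500, and 180 protects 150 completers only up to 16.7% loss

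*Combined protocol and SAP*

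**What the plan says.** All the figures are in the Sample Size section of the combined protocol and SAP.

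- The power calculation arrives at 150 children, 75 per group.
- The section then assumes 10% prevalence of NAID and states that "screening approximately 1500 children will identify 150 children with NAID to be randomized over a 4 year period".
- The allowance for losses follows: "Expecting potential drop-outs and withdrawals to be 0-20% a total of 180 NAID children will be randomized".
- A little further on, the iron deficiency anemia (IDA) group is sized from the earlier cohort: "From the screening cohort of 1500 it is anticipated that 1-2% will have IDA (n=25").

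Three other places bear on these numbers.

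- Participant Timeline makes entry depend on family agreement and a further visit: "those who agree to participate in the OptEC trial will be asked to come back to the physicians office". Recruitment Strategy adds a telephone invitation and written consent. Neither section gives an expected consent rate.
- Statistical Analysis sets a threshold for extra analysis: "If >20% of participants are lost to follow-up a per protocol analysis will be carried out", in addition to the intention-to-treat analysis.
- Sub-study #1, the internal pilot, says that "the sample size may be recalculated after 30 participants have been enrolled in the randomized trial".

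**The concern.** Both 150 and 180 are described as children to be randomized, and both are set against the same 1500 screened. At the stated prevalence, 1500 can supply only the smaller number, and then only if no eligible family declines. It appears that the screening number was not carried forward when the loss allowance was added.

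The allowance itself also looks wrong. Multiplying the required number by one plus the loss rate gives too few; the required number has to be divided by one minus the loss rate. The protocol's range of expected losses runs up to 20%, and its per-protocol trigger starts only above 20%. Losses between 16.7% and 20% are therefore within what the plan treats as expected, yet they leave fewer than 150 children.

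At stake is whether the practices and the funding are planned for the screening effort that 180 requires. If 1500 were in practice used as the stopping point, the trial would fall well below the number on which its power statement rests.

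**Working it through.** **Inputs from the documents.** Required total 150 (75 per group); difference 6 points, SD 15, power 80%, significance level 5%; prevalence 10%; screened 1500; losses 0–20%; randomized 180; IDA 1–2% (all Sample Size). The primary analysis is ANCOVA on baseline (Statistical Analysis). The baseline to 4-month correlation is not given; the internal pilot is to estimate it.

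**Assumptions made here.** Consent of 100%, 90% and 80%; correlation r of 0.5, with 0.4 to 0.6 as the range; two-sided testing.

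**1. Reproducing the plan's figures.**
- Screening: 1500 × 0.10 = 150. This matches the first number to be randomized.
- Loss allowance: 150 × 1.20 = 180. This matches the second.

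**2. Loss allowance.**
- Number needed to keep 150 at 20% loss: 150/(1 − 0.20) = 187.5, so 188.
- Largest loss at which 180 still leaves 150: 1 − 150/180 = 16.7%.
- Completers from 180:

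| Loss | Completers |
|---|---|
| 10% | 162 |
| 15% | 153 |
| 16.7% | 150 |
| 20% | 144 |

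**3. Screening needed for 180 at 10% prevalence**, as 180/(0.10 × consent rate):
- 100% consent: 180/0.10 = 1800
- 90% consent: 180/0.09 = 2000
- 80% consent: 180/0.08 = 2250

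Conversely, 1500 screens supply 180 only if prevalence × consent reaches 180/1500 = 12%. That means 12% prevalence with full consent, or 0.12/0.8 = 15% at 80% consent.

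**4. Could prevalence be higher than 10%?** Appendix 2 gives ferritin quartiles of 15.55, 23.5 and 36.7 µg/L for ages 12–36 months. A lognormal fitted to these (an assumption) has a log-SD of 0.637 and puts 14.0–14.6% at or below 12 µg/L. Removing 1–2% for IDA leaves about 12.0–13.6%. From 1500 screens that is 1500 × 0.120 = 180 to 1500 × 0.136 = 204 at full consent, and 144 to 163 at 80% consent. Against this, the Background section cites US figures of 9% for iron deficiency and 3% for IDA. If IDA is counted within iron deficiency, these imply about 6% NAID.

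**5. Power for 6 points.** ANCOVA, residual SD = 15 × √(1 − r²), non-central t, two-sided 5%, one degree of freedom spent on baseline:

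| Completers per group | Situation | r = 0.4 | r = 0.5 | r = 0.6 |
|---|---|---|---|---|
| 75 | 150 as planned | 75.7% | 80.2% | 86.0% |
| 72 | 180 randomized, 20% lost | 73.9% | 78.6% | 84.6% |
| 60 | screening ended at 1500, 20% lost | 65.9% | 70.9% | 77.5% |

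The last row uses 1500 × 0.10 × 0.80 = 120 completers.

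**6. IDA group.** 1–2% of 1500 is 15–30, and 1–2% of 1800 is 18–36. The stated 25 fits either cohort.

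**The case against.** The section can be read in order: 150 needed for analysis, about 1500 screened to find them, then inflation to a final 180. On that reading the operative target is clear, and the second mention of 1500 only sizes the IDA and iron-sufficient groups. Nothing in the protocol caps screening at 1500, and Trial Monitoring foresees no early termination, so the 60-per-group case is hypothetical. Its 120 would be completers, and not necessarily the analysis set, because Statistical Analysis keeps all randomized children and allows imputation. The network's own ferritin data suggest that 1500 might supply 180 before refusals. The internal pilot also lists pre-randomization feasibility among its objectives, which could cover yield and consent. Finally, the drop-out slip amounts to six children.

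Most of this limits the consequence and does not remove the inconsistency. The text describes 150 as the number to be randomized, not as the number to be analysed, and at the printed 10% prevalence 1500 cannot yield 180 on any reading. If prevalence is higher, the 10% is the figure to correct, and refusals could still take the yield below 180. The pilot's recalculation is optional, its statistical aims are variance and correlation, and no section says that it revisits prevalence, screening or the loss allowance. Imputation does not restore lost information. The points that stand are that the shortfall is conditional and that the loss slip alone is minor.

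**Conclusion.** The concern holds. The Sample Size section gives two numbers to be randomized against one screening cohort that supplies only the smaller. For 180 at 10% prevalence the stated screening number is short by at least 300 children (1800 against 1500), and by 750 at an assumed 80% consent. The loss allowance covers losses up to 16.7%. At the 20% end of the stated range it leaves 144 children, 6 fewer than required, at a cost of 1.6 power points at r = 0.5.

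This is an under-stated workload and a sample-size paragraph that does not add up; it is not a demonstrated loss of power. Power of about 71% arises only if screening stops at 1500, prevalence is 10%, all eligible families consent, 20% are lost and r is 0.5. The yield calculation depends on prevalence, for which the documents point both above and below 10%.

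The check takes 150 as given. From the stated inputs alone, an unadjusted two-sided comparison needs 198 (99 per group); 150 is reached under ANCOVA with a correlation of about 0.49, which the documents do not state. If 150 were revised, every figure above would move with it, but the mismatch would remain.

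**What to change.** Rewrite the Sample Size section so that its figures agree. Suggested text:

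*A total of 180 children with NAID will be randomized. This retains 150 completers for losses up to 16.7%; at 20% loss, 144 would remain (188 would be needed to retain 150). At 10% prevalence, at least 1800 children must be screened before allowing for refusals; in general the number is 180/(0.10 × consent rate), for example 2250 at an assumed consent rate of 80%.*

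State the consent rate that the sponsor actually assumes, and use the resulting screening number in both places where 1500 now stands. If the sponsor prefers to keep 1500 because the network's data support a higher prevalence, change the 10% and show that prevalence × consent reaches 12%. The IDA figure of 25 can stay.

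The cost is wording. The estimand, the analysis and the target of 180 do not change. At 10% prevalence, the stated screening workload rises from about 1500 to at least 1800.
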